Blood draw for lab assessments (abbreviated chemistry panel) has to be done. In case of lab deviations an unscheduled visit may be scheduled at the discretion of the investigator to re-

assess lab parameters and evaluate the efficacy of taken measures. Please refer to Appendix 1, Appendix 2, Appendix 3, and Appendix 4, respectively, for guidance on handling hyperkalemia, hypotension, and renal dysfunction.

Visit 6 (+6 weeks)

After 6 weeks of treatment, patients will be checked for tolerability at Visit 6. Every attempt should be made to keep the patients stable on level 3 in accordance with all safety parameters (e.g. symptomatic hypotension, renal dysfunction and /or hyperkalemia).

[REDACTED]

Ergospirometry will be performed at Visit 6 (according to a separate manual). Patients will be under continuous ECG and frequent blood pressure monitoring.

[REDACTED]

Plausibility and quality checks of the ergospirometry data will be done by a reading center. If ergospirometry data acquisition fails for any reason, it may be repeated one day later.

[REDACTED]

Blood draw for lab assessments (abbreviated chemistry panel) has to be done. In case of lab deviations an unscheduled visit may be scheduled at the discretion of the investigator to reassess lab parameters and evaluate the efficacy of taken measures. Please refer to Appendix 1, Appendix 2, Appendix 3, and Appendix 4, respectively, for guidance on handling hyperkalemia, hypotension, and renal dysfunction.

Visit 7 (+3 months; EOS)

After 3 months of treatment, a final assessment of patients for tolerability at Visit 7 is performed.

[REDACTED]

Ergospirometry will be performed at Visit 7 (according to separate manual). Patients will be under continuous ECG and frequent blood pressure monitoring.

Plausibility and quality checks of the ergospirometry data will be done by a reading center. If ergospirometry data acquisition fails for any reason, it may be repeated one day later.

Blood draw for final laboratory assessments has to be done.

Unscheduled visits

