*** Patients who prematurely discontinue study treatment should also return for the end of study (EOS) to collect at least safety assessments indicated by three asterisks (***).

**** To be documented at Visit 7 or at the time of premature discontinuation

1 Complete physical examination required at Visits 1, 2 and 7 (end-of-study visit). Short physical exam is sufficient at Visit 3 -6.

2 Qualifying LVEF measurements/documentation of structural heart disease will be based on obtained measurements (e.g. echocardiograms (echo)) performed ≤ 6 months prior to Visit 1. If an assessment performed ≤6 months prior to Visit 1 is not available, an echo must be performed during the screening epoch.

3 Women of childbearing potential only. At Visit 1 and 7 and in case of a positive urine pregnancy result, a confirmatory serum pregnancy test has to be performed at the central laboratory. A urine pregnancy test will be performed locally at Visit 2 and 7 and every time this is clinically indicated or a contraception gap has been reported.

4 Abbreviated chemistry panel including potassium, BUN, and serum creatinine will be measured at interim visits at the central laboratory.

5 Screening ECG performed within the 6 months before Visit 1 is accepted.

Phase		Screening		Double blind treatment**				
Visit	D/S*	1	2**	3**	4**	5**	6**	7/EOS***
Days(D)/ Weeks (W)		D-16 to -12 W-2	D-9	D1	D14 W2	D28 W4	D42 W6	D84 W12

9 At Visit 3 and 4, patients should come to the site 3 to 4 days prior to the scheduled visit date for blood draw only so that results from central laboratory are available and enable a competent decision on randomization or up-titration at the respective visits.

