6.5.4 Laboratory evaluations

A central laboratory will be used for analysis of all collected specimens. Details on the collections, shipment of samples and reporting of results by the central laboratory will be provided to investigators in the laboratory manual.

Clinically notable laboratory findings are defined in Appendix 1.

Full laboratory evaluations (hematology, blood chemistry, and urine for pregnancy assessment in child-bearing women; Table 6-2) for the assessment of safety in this study will be performed at Visits 1, 2 and 7. Electrolyte laboratory evaluations will be included in the abbreviated laboratory assessments at Visits 4 to 6.

The investigator or his/her designee should review the central laboratory results as soon as they become available to decide on whether any adjustments in the patient's study drug or non-study

drug regimen are needed. Therefore unscheduled visit are possible based on investigator's discretion.

All central laboratory results will be communicated to the investigators and the sponsor. Details on the collection, shipment of samples and reporting of results by the central laboratory will be provided to investigators in the laboratory manual.

Laboratory values that exceed the boundaries of a notable laboratory abnormality must be commented on by the investigator in the Comments screen of the patient's eCRF and additional laboratory evaluations should be performed, as judged appropriate by the investigator. If the laboratory abnormality induces clinical signs or symptoms, or requires therapeutic intervention, then the diagnosis or medical condition must be entered on the AEs screen of the patient's eCRF. If the laboratory abnormality is the primary reason for an unforeseen hospitalization or otherwise fulfills the seriousness category of an AE, then the procedure for rapid notification of SAEs must be followed. Likewise, if the laboratory abnormality leads to discontinuation from the study drug (temporarily or permanently), the patient must be followed until the abnormality resolves or until it is judged to be permanent.

Table 6-2 Routine laboratory examination

Hematology*	Biochemistry*	Urine measurements
Red Blood Cells count	Glucose	Urine pregnancy test at Visit 2 and 7 and when clinically indicated or a contraception gap has been reported
White Blood Cells count	Sodium	
Platelet Count	Potassium **	
Hemoglobin	Chloride	
Hematocrit	Calcium	
WBC differential	Blood urea nitrogen (BUN) **	
	Creatine kinase (CK)	

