2.8.3 Laboratory data

Laboratory data will be summarized for double blind period based on the SAF and also be listed.

Laboratory data for hematology (including hemoglobin, hematocrit, red blood cell count(RBC), white blood cell count with differential (WBC), and platelet count), and blood chemistry (including Blood urea nitrogen (BUN), glucose, creatinine, total bilirubin, AST (SGOT), ALT

(SGPT), alkaline phosphatase, sodium, potassium, chloride, calcium, HbA_{1c}, total protein, albumin, uric acid, and lipid profile, estimated glomerular filtration rate (eGFR)) will be summarized by treatment.

The eGFR is calculated according to the formula:

$$\text{eGFR (mL/min/1.73 m}^2\text{)} = 175 \times (\text{Serum creatinine}/88.4)^{-1.154} \times (\text{Age})^{-0.203} \\ \times (0.742 \text{ if female}) \times (1.212 \text{ if black}),$$

where serum creatinine is in $\mu\text{mol/L}$ (SI unit) and age is non-rounded at the time of the laboratory sample in years.

Descriptive summary statistics (mean, median, standard deviation, min and max) for the change from baseline to each study visit will be presented. These descriptive summaries will be presented by laboratory test and treatment group. Change from baseline will only be summarized for subjects with both baseline and post-baseline values and will be calculated as defined in section 2.1.1.

The number and percentage of subjects with clinically notable laboratory results after baseline will be presented. Clinically notable laboratory results, for those parameters where ranges are available, are given in [appendix 1](#) below. For the calculation the denominator are based on the evaluable post-baseline subjects who did not have the notable abnormality at baseline from the central laboratory.

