2.8.3.2 Clinical chemistry

Blood Chemistry tests performed may include the following:

- Blood urea nitrogen (BUN)
- Creatine kinase (CK)
- Glucose
- Creatinine
- Total bilirubin (TBL)
- AST (SGOT)
- ALT (SGPT)

- Alkaline phosphatase (ALP)
- Sodium
- Potassium
- Potassium
- Calcium
- Hemoglobin A1C
- Total protein
- Albumin
- Uric acid
- Lipid profile

The above tests will be analysed at visit 1 and 7.

- Thyroid-stimulating hormone (TSH) will be assessed at Visit 1 only.

BUN, serum potassium, and serum creatinine value for eGFR calculation will be obtained from patients at every visit when a complete laboratory test is not done (i.e., Visits 3-5).

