Appendix 3: Guidelines for the management of renal dysfunction

General principles:

Glomerular filtration rate in HF patients depends on intrinsic renal function and on a balance between afferent and efferent glomerular arterial tonicity. This tonicity is partly regulated by a stimulation of angiotensin II and could be affected by either study medication. Moreover, renal dysfunction may develop or may deteriorate in some patients after study drug administration. These recommendations have been developed to guide the investigators in managing patients with renal dysfunction after randomization.

Two types of response to serum creatinine increase are described:

Surveillance situation

If, at any time after randomization, eGFR decreases by $\geq 25\%$ from baseline (Visit 2) (or if serum creatinine concentration increase to 2.5 mg/dL [221 μ mol/L]), the investigator will check for potentially reversible causes of renal dysfunction such as:

- Non-steroidal anti-inflammatory drug intake, antibiotics, or other treatments known to affect creatininemia
- Volume decrease, including that resulting from excessive dosing of diuretics
- Urinary infection
- Urinary tract obstruction
- Study medication

Action situation

If a patient eGFR decreases by $\geq 40\%$ from baseline (Visit 2) (or if serum creatinine concentration rises above 3 mg/dL (265 μ mol/L)), the investigator will check for potentially reversible causes of renal dysfunction (see above).

If the investigator judges that study medication has to be stopped, he/she will have to contact the Novartis medical monitor or his/her designee. Thereafter, serum creatinine assessments will have to be repeated at least each week until levels return to acceptable values. If study medication was stopped, every effort will be done to restart it again, according to clinical conditions.

Appendix 4: Treatment guidelines for hyperkalemia (serum potassium greater than or equal to 5.3 mmol/L)

General principles

Elevation of potassium levels above the predefined values should be repeated and confirmed before any action is taken.

Any patient with a serum potassium ≥ 5.3 mmol/L after enrollment into the study requires regular, repeated checks of potassium concentration (beyond that prescribed in the protocol) until it is clear that the potassium concentration is stable and not rising into the range of concern (≥ 5.5 and < 6.0 mmol/L) or potential danger (≥ 6.0 mmol/L).

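### SAP 2.8.3.1 and 2.8.3.2 name the wrong laboratory analysis visits: Visits 1 and 7 omit the baseline draws and the interim potassium, BUN and creatinine draws, and the range Visits 3-5 omits Visit 6

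*SAP*

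**What the plan says.** SAP 2.8.3.2 lists the chemistry tests, among them BUN, creatinine and potassium, and then says "The above tests will be analysed at visit 1 and 7". SAP 2.8.3.1 repeats that sentence for hematology. SAP 2.8.3, the parent section, says that descriptive statistics "for the change from baseline to each study visit will be presented".

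SAP 2.8.3.2 closes by saying that BUN, potassium and creatinine are obtained "at every visit when a complete laboratory test is not done (i.e., Visits 3-5"; protocol 6.5.4.2 has the same sentence. Other parts of the protocol differ:

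- Protocol 3.1, under Visit 6: "Blood draw for lab assessments (abbreviated chemistry panel) has to be done".
- Protocol 6.5.4: "Electrolyte laboratory evaluations will be included in the abbreviated laboratory assessments at Visits 4 to 6".
- Protocol Table 6-1 marks the abbreviated panel at Visits 3, 4, 5 and 6. Its footnote 4 reads: "Abbreviated chemistry panel including potassium, BUN, and serum creatinine will be measured at interim visits at the central laboratory".
- Protocol 6.5.4.1, 6.5.4.2 and Table 6-1 place the complete panel at Visits 1, 2 and 7.

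On baseline, SAP 2.1.1 takes the last non-missing value before first dose unless another rule is given. SAP Appendix 3 gives one for renal function, measuring the eGFR fall "from baseline (Visit 2) (or if serum creatinine concentration increase to 2.5 mg/dL".

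The SAP 2.8.3.2 list also names potassium twice and omits chloride, which SAP 2.8.3 and SAP Appendix 1 both include.

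**The concern.** Hyperkalemia and renal dysfunction are named safety assessments in the protocol synopsis, and the interim draws exist to watch for them during and after up-titration. A programmer who takes SAP 2.8.3.2 at its word would build by-visit tables with a screening value and an end-of-study value and nothing between.

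Such a table would be least informative where it matters most. Under SAP Appendix 4, a patient with potassium of 6.0 mmol/L or more stops study drug at once. Under Table 6-1, "Patients who prematurely discontinue study treatment should also return for the end of study (EOS) to collect at least safety assessments". If the stop is permanent, that patient's end-of-study potassium is an off-drug value, so a by-visit table restricted to Visits 1 and 7 could show recovery and not the rise that led to the stop.

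The starting point is also wrong. Visit 1 is a screening value that later pre-dose draws supersede under the SAP's own baseline definition.

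**Working it through.** The plan states no figure to reproduce here. The check sets the visit lists side by side and counts draws.

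**Schedule for potassium, BUN and creatinine** (Table 6-1 and its footnote 9; protocol 3.1)

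| Visit | Nominal day | Panel | In SAP 2.8.3.2 (Visits 1 and 7)? |
|---|---|---|---|
| 1 | -16 to -12 | complete | yes |
| 2 | -9 | complete | no |
| 3 | 1 (blood 3 to 4 days earlier) | abbreviated | no |
| 4 | 14 (blood 3 to 4 days earlier) | abbreviated | no |
| 5 | 28 | abbreviated | no |
| 6 | 42 | abbreviated | no |
| 7 | 84 | complete | yes |

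**Counts**

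- All scheduled draws: 3 complete + 4 abbreviated = 7. Visits 1 and 7 cover 2 of 7.
- Post-dose draws: Visits 4, 5, 6 and 7 = 4. The list keeps 1 and omits 3, and 3/4 = 75%. At the planned 100 patients per arm that is 3 x 100 = 300 of 4 x 100 = 400 scheduled values per arm, on the literal reading only.
- Timing: Visit 4 blood is taken at about Day 10 to 11 (14 - 4 to 14 - 3), before the Day 14 up-titration. The scheduled draws after up-titration are therefore Visits 5, 6 and 7. On the literal reading the first of these to be summarised is at Day 84, which is 84 - 14 = 70 days after up-titration.

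**Baseline**

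- For tests in the complete panel only, and for hematology, the last pre-dose draw under SAP 2.1.1 is normally Visit 2.
- For potassium, BUN and creatinine it is normally the draw for Visit 3.
- For the Appendix 3 eGFR criteria it is Visit 2 by explicit statement, which SAP 2.1.1 allows.
- Visits 1 and 7 include neither Visit 2 nor the Visit 3 draw: 0 of 2.

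**The range Visits 3 to 5**

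The rule covers every visit without a complete panel. Complete panels fall at Visits 1, 2 and 7, so the remaining visits are 3, 4, 5 and 6. The stated range covers 3 of these 4 and contradicts the rule it illustrates.

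**Do the other outputs fill the gap?**

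- SAP 2.8.3 counts notable results after baseline with no visit limit. The Appendix 1 potassium criterion is a rise of more than 20%. A potassium of 6.0 meets it from any baseline below 5.0, because 5.0 x 1.20 = 6.00.
- Entry allows potassium up to 5.2. From 5.0 the rise to 6.0 is exactly 20%, which is not more than 20%. From 5.2 it is (6.0 - 5.2)/5.2 = 15.4%. A mandatory-stop value of 6.0 reached from a baseline of 5.0 to 5.2 is therefore not flagged.
- SAP 2.8.3.4 analyses potassium of 5.3 or more, creatinine and eGFR by reference to Appendices 3 and 4. It has no visit limit and uses absolute cut-offs, so it can capture such a case. Those appendices are management guidance and name no analysis visits.

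**The case against.** The strongest reply is that SAP 2.8.3.2 is mainly a sampling schedule modelled on protocol 6.5.4.2. It speaks of tests performed, of TSH assessed at one visit, and of values obtained at interim visits. On that reading Visits 1 and 7 is the complete-panel schedule with Visit 2 dropped by accident, the closing sentence restores the interim draws, and SAP 2.8.3 governs what is tabulated.

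Much of this stands. The reading is plausible, so it is too strong to say that the two sections cannot be reconciled. The 1-of-4 count belongs to the literal reading and is not a settled loss of data. The notable-value counts and the SAP 2.8.3.4 analyses are real backstops.

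Some of it does not stand. Even as a sampling schedule the sentence is wrong, because Visit 2 is missing. It says analysed, whereas the closing sentence says only when samples are obtained, and that sentence still omits Visit 6. The SAP does not say that 2.8.3 overrides its subsections. SAP section 4, which lists changes to protocol-specified analyses, mentions no reduction in laboratory visits, so this is not a declared choice.

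A reader might go further and infer that interim hyperkalemia or renal events would vanish from the report. The documents do not support that: no text links the visits in 2.8.3.2 to the notable-value counts, the 2.8.3.4 analyses, the listings or the adverse event tables.

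A reader might also infer that sites will skip the Visit 6 draw, stretching the longest scheduled interval between checks from 84 - 42 = 42 days to 84 - 28 = 56 days. A site would have to disregard Table 6-1, protocol 3.1 and protocol 6.5.4 to do so, which is unlikely.

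**Conclusion.** The visit lists are wrong as written; this is more than missing detail. Severity is at the low end of minor.

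The inconsistency itself rests on no assumption and follows from comparing the two documents. Its size depends on the reading. Taken literally, the by-visit potassium, BUN and creatinine summaries keep 1 of 4 scheduled post-dose draws and compare it with a superseded screening value. Taken as a sampling schedule governed by SAP 2.8.3, the interim values remain, and the harm is an ambiguous specification with Visits 2 and 6 missing from its lists.

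On either reading the effect is limited to descriptive by-visit safety tables. Interim events can still appear through the other safety outputs, with the narrow exception in the notable-value count for a potassium rise to 6.0 from a baseline of 5.0 to 5.2. The efficacy analyses are untouched.

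**What to change.** 1. In SAP 2.8.3.1 and 2.8.3.2, state that hematology and the complete chemistry panel are summarised at Visits 1, 2 and 7, and that potassium, BUN, creatinine and eGFR are summarised at every visit from 1 to 7. TSH stays at Visit 1 only.
2. In the same place, state that change from baseline follows SAP 2.1.1, with Visit 2 as the reference for the Appendix 3 eGFR criteria.
3. Change the range Visits 3-5 to Visits 3-6 in SAP 2.8.3.2 and protocol 6.5.4.2.
4. In the SAP 2.8.3.2 list, replace the second potassium entry with chloride.

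The cost is wording in two SAP subsections and one visit range in the protocol. No new data are needed, because every draw is already scheduled. The protocol edit needs a written amendment under protocol 11.1, but the SAP correction need not wait for it.

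A count by arm of the worst post-dose value in the Appendix 3 and 4 categories would be a useful option in SAP 2.8.3.4, partly because it would catch the 5.0 to 5.2 baseline case. It is an added output and is not needed to correct the error. It would also include unscheduled samples, so an arm sampled more often could show more events; the by-visit table of scheduled values should sit beside it.

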2.8.3.3 Liver event

Liver event data of sign and symptoms will be summarized and listed based on data collected on eCRF. Analysis will be based on SAF.

Liver events –imaging will be listed based on SAF.

2.8.3.4 Specific laboratory data

Liver function test (LFT) data will be analyzed according to what specified in hepatotoxicity in [appendix 2](#) in [section 5](#).

Laboratory data related to renal dysfunction (serum creatinine, eGFR) will be analyzed according to what specified in renal dysfunction in [appendix 3](#) in [section 5](#).

Laboratory data related to hyperkalemia (serum potassium greater than or equal to 5.3 mmol/L) will be analyzed according what specified in [appendix 4](#) in [section 5](#).

2.8.4 Other safety data

2.8.4.1 ECG and cardiac imaging data

Not applicable.

2.8.4.2 Vital signs

Sitting systolic blood pressure (SSBP), sitting diastolic blood pressure (SDBP), sitting pulse rate and body weight will be summarized by treatment group and visit, including changes from

baseline. Summary statistics will be based on SAF. Where the baseline is defined as visit 2 and double blind period is from visit 3 to visit 7.

Change from baseline will only be summarized for subjects with both baseline and post-baseline values and will be calculated as defined in [section 2.1.1](#).

2.8.4.3 Height and Weight and waist hip circumference

Height (cm), Body weight (kg), Waist/hip circumference (cm) will be summarized by treatment group and visit, including changes from baseline using SAF.

Change from baseline will only be summarized for subjects with both baseline and post-baseline values and will be calculated as defined in [section 2.1.1](#).

2.8.4.4 NYHA Class assessment

Patients' NYHA class will be assessed at baseline and post-baseline. At baseline, only patients with heart failure NYHA class III can be enrolled in the study. The total number and percentage of patient with each NYHA class will be provided by treatment group and visits based on SAF. The change in NYHA class at every post-baseline visit compared to baseline will be summarized by frequency distribution.

2.9 Pharmacokinetic endpoints

Not applicable.

2.10 PD and PK/PD analyses

Not applicable.

2.11 Ergospirometry analysis

Ergospirometry data will be summarized for visit 2 (baseline), visit 6 and visit 7.

The data will be collected for the below parameters:

- VO_{2peak} adjusted
- [REDACTED]
- VE/VCO₂
- Exercise capacity (Watt) at VAT
- [REDACTED]
- [REDACTED]
- [REDACTED]

Descriptive summary statistics (mean, median, standard deviation, min and max) for baseline (visit 2) and change from the baseline to visit 6 and visit 7 will be presented. The descriptive summaries will be presented by ergospirometry parameters and treatment group based on FAS. Change from baseline will only be summarized for subjects with both baseline and post-baseline values and will be calculated as defined in [section 2.1.1](#).

[figure not shown]
Reason for termination will also be summarized separately based on FAS.

[figure not shown]

[figure not shown]
2.13 Borg scale analysis

[figure not shown]
Borg scale data will be summarized for visit 2 (baseline), visit 6 and visit 7.

[figure not shown]
Descriptive summary statistics (mean, median, standard deviation, min and max) for the baseline and change from the baseline to visit 6 and visit 7 will be presented. The descriptive summaries will be presented by treatment group. Change from baseline will only be summarized for subjects with both baseline and post-baseline values and will be calculated as defined in [section 2.1.1](#). Maximum value among the timepoints at every visit will be used for the analysis. In case of multiple maximum values at the same visit, the most recent timepoint will be considered in the analysis. Listings will be provided with all the timepoint values at all visits.

[figure not shown]

[figure not shown]

